#### **RESEARCH PROTOCOL SUMMARY**

TITLE:	Comparison of devices for the detection of diabetic neuropathy; an
	evaluative diagnostic study.
Short title:	'MANDARIN', Medipin Assessment for Neuropathy in Diabetes, A
	Real-world INvestigation
IRAS number	325532
Device description	CE-marked neuropathy test device: Medipin (MHRA No. 1321)
	Medipin is a single-use precision instrument designed to optimise cutaneous pinprick perception. Medipin's protected point is designed to significantly enhance pinprick acuity to achieve useful stimulation and reduce risk of damaging delicate skin. The protective annulus inhibits depth of penetration and protects against self-inflicted "needle stick" injury.
Study design	Prospective, single-centre, controlled, non-randomised, evaluative diagnostic study
Primary objective	Respective detection rate of diabetic neuropathy determined by use of Medipin and standard care device (10g monofilament). Pragmatic real- world approach using only devices utilised in standard primary care based clinics.
Secondary objectives	Evaluation of feasibility that a 10-point scale can be applied for Medipin in relation to degree of neuropathy, as opposed to standard yes/no quantification.
	concordance between wealpin and rog monomament test results.
	Relative performance/concordance achieved with 10g monofilament depending on number of tests and locations included in the assessment.
Inclusion & Exclusion	Inclusion criteria:
criteria	
 
Adult patients aged ≥ 18 years
 

	- Patients with type I or type II diabetes mellitus
	Exclusion criteria:
	
 
Aged < 18 years
 
Any reasons for the patient being unable to follow the protocol, including lack of mental capacity to consent to taking part in the study (examples include dementia, severe learning disability).
 
The patient has concurrent (medical) conditions that in the opinion of the investigator may compromise patient safety or study objectives (examples include receiving palliative care, active cancer treatment)
 

	- Amputation of a lower limb
	
 
Confirmed and ongoing foot wound / ulcer
 

Sample size	Sample size determined for prevalence study, with predetermined criteria
-	of 10% prevalence (can be either based on Medipin or monofilament
	testing), a population of 160,000, 95% confidence interval, and precision of
	5%. The required initial sample size is 139 patients.
	Potential to expand to 552 patients if 2.5% precision applied.

#### Lay Summary

Nerve damage and loss of protective sensation (LOPS) is a complication of diabetes. This diabetic neuropathy (DN) can subsequently lead to further complications such as diabetic foot ulcers and even amputation of toes and lower limbs. It is therefore essential to monitor for the development of DN in diabetic patients. In standard clinical practice DN is checked for using a monofilament, a piece of nylon on a stick that is pushed onto the patient's foot; LOPS is the sign of DN having developed. Monofilament testing checks for damage to large nerve fibres. There is however evidence that small nerve fibres are damaged before the large nerves are affected. Using a practical, reliable, and simple tool to check for small nerve damage in a clinic setting may aid in detecting LOPS/DN earlier and optimising patient management. Medipin is a hygienic single-use device designed to check for small nerve fibre damage in feet. The main objective of this study is to determine how many patients have LOPS/DN when tested with the monofilament and Medipin device respectively and to what degree there is an overlap between the two tests. For this purpose a total of 139 patients will be assessed at a single clinic visit.

#### 1 BACKGROUND AND RATIONALE

Diabetes is a chronic condition that can lead to multiple complications affecting various organs, including of the lower limbs. Initial nerve damage in the patient's foot results in loss of protective sensation, diagnosed as diabetic neuropathy (DN). Due to reduced sensation in the feet, patients may walk on a stone stuck in their shoe or not realise foot skin has been damaged; this can then result in ulceration. Poor healing associated with diabetes – because of vascular damage – can then lead to infection and amputation.

Diabetic foot ulcers are the most common type of foot ulcer and are associated with significant health and cost implications. Whereas costs for foot ulcer care were £300m in 2005-06, this had risen to ~£900m to care diabetes related ulceration and amputation care in 2014–15 (Posnett & Franks 2008; Kerr et al, 2019). In the United States, neuropathy is implicated in up to 80% of >50,000 amputations (Smieja et al, 1999). Large studies conducted in Europe in the mid-90s estimated a prevalence of diabetic neuropathy of circa 25% (Young et al, 1993; Tesfaye et al 1996; Cabezas-Cerrato et al 1998). In a more recent study where 10g monofilament testing was utilised, 11.7% of women with normal fasting glucose, 14.4% of women with impaired fasting glucose (IFG), and 18.3% of women with diabetes had LOPS (Ylitalo et al, 2013). It is imperative to ensure DN is diagnosed early in diabetes patients and that they are educated to look after their feet, thereby minimising the risk of further costly and serious complications.

In regular clinical practice, the use of a 10g monofilament is the mainstay for DN diagnosis. The 10g relates to the amount of g-force applied to the skin with the nylon strand attached to a handheld stick. More sensitive tests are available, including nerve conduction tests and biopsy of skin tissue, but monofilaments are used since they are relatively effective in detecting DN and because the test is affordable, plus straightforward to apply and interpret. Two types of nerves are present in the skin, and diabetes related damage can lead to a) large fibre neuropathy: manifests with the loss of joint position and vibration sense and sensory ataxia, and b) small fibre neuropathy: manifests with the impairment of pain, temperature and autonomic functions. Monofilament application, akin of stroking the skin, tests predominantly for large fibre DN. This means that small fibre damage is usually not specifically tested for. For example, Ylitalo et al (2013) only considered small fibre damage with the Michigan Neuropathy

Screening Instrument (MNSI) symptom questionnaire, not through a physical assessment as done for large fibres with the monofilament device. Of interest is that there were no statistically significant differences in the prevalence of monofilament insensitivity between non-diabetics and diabetics, also observed by Gregg et al (2007), but the prevalence of peripheral neuropathy symptoms (which includes questions regarding small fibre damage) did increase significantly with fasting glucose categories. There is evidence that small fibre damage develops before large fibre damage manifests, which may be of value if early intervention and prevention for DN is the goal (Malik et al, 2011; Ponirakis et al, 2014; Breiner et al, 2014). Recently, Burgess et al (2021) stated "DN is diagnosed at a late, often pre-ulcerative stage due to a lack of early systematic screening and the endorsement of monofilament testing which identifies advanced neuropathy only".

Apart from the issue of which nerve fibre type response to test for, another issue in DN diagnostics is the variability in approach with the 10g monofilament. Dros et al (2009) highlight this: 'Another problem is the lack of standardization of the monofilament test methods. Different methods are described varying from 1 testing site to 10 testing sites on 1 foot, and there is no evidence or consensus about the most appropriate threshold'. National clinical guidelines unfortunately do not settle the matter either. NICE gives no detailed guidance on how to assess for diabetic neuropathy. In their NICE guideline (26 August 2015, www.nice.org.uk/guidance/ng19) they only mention the following:

Assessing the risk of developing a diabetic foot problem. 1.3.4 When examining the feet of a person with diabetes, remove their shoes, socks, bandages and dressings, and examine both feet for evidence of the following risk factors: neuropathy (use a 10 g monofilament as part of a foot sensory examination)

The end result is that different NHS Trusts use different methods to determine if a patient has DN. Appendix 1 gives an overview with some examples. A review by Feng et al (2009) concluded: "To maximize the diagnostic value of SWME (Semmes Weinstein monofilament examination), a three site test involving the plantar aspects of the great toe, the third metatarsal, and the fifth metatarsals should be used. In the group with history of ulceration as the reference test, the four studies that used only one site had a sensitivity of around 50%, considerably lower than other studies that tested more than one site. Testing more sites allowed the SWME to be more sensitive in identifying patients with Diabetic Peripheral Neuropathy". Unfortunately, Feng and colleagues did not specify what total score of such an investigation would be deemed presence of DN. Furthermore, the references they cited for the rationale for the three anatomical sites did not actually use that exact same methodology (they measured either eight different sites, or six with one of them being the heel rather than the great toe). It is also recognized that monofilament diagnostics can be influenced by a number of variables, including the operator, how often the monofilament has been used previously, and even weather conditions (Haloua et al, 2011).

The use of a pinprick has been advocated in the past and utilized in research studies (Abbott et al,2002; Boulton et al 2008). In those studies, it was shown that inability to perceive the pinprick challenge is significantly associated with a risk of developing ulcers. However, the test does not tend to feature in current NHS guidance on screening for DN. One reason may be that in the past very rudimentary or home-made pinprick device were utilized in the absence of a fit-for-purpose device. Unlike with testing for large fibre nerve damage using the reusable monofilament device, testing for small fibre damage requires more force and therefore should always be conducted using a single use disposable device. Devices like Medipin and also Neurotips (the latter being twice the price per unit compared to the former) meet those criteria. To illustrate past suboptimal practice, in one paper by Smieja et al (1999) the following approach was taken: "Pinprick sensation was tested with a sterile or unused safety pin over the plantar aspect of the distal first, third, and fifth toe of each foot with the stimulus applied once per site. Patients were asked to identify when they felt a sensation, and whether it was sharp or dull. Findings were scored as sharp, dull, or absent for each site".

Taken together, there is a lack of evidence concerning the use of affordable and easy-to-apply devices to diagnose small fibre DN in a real-world community setting. This study will determine the prevalence of small nerve damage using the Medipin device, and compare this to large fibre nerve damage as measured with a 10g monofilament device. Two approaches for monofilament testing will be taken, to take into account a) the variability in standard NHS practice and literature around number and locations tested b) the dorsal approach taken with the Medipin device.

#### 2 OBJECTIVES

#### 2.1 PRIMARY OBJECTIVE AND OUTCOME MEASURES

Respective detection rate of diabetic neuropathy determined by use of Medipin and standard care device (10g monofilament). Pragmatic real-world approach using only devices utilised in standard community based clinics.

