#### Table 2, Overview of comparison between two neuropathy tests

Test result	Medipin: patient reaction	Medipin: patient reaction absent
	present	
10g monofilament*: patient reaction present	No sign of neuropathy	Only small fibre neuropathy
10g monofilament*: patient reaction absent	Only large fibre neuropathy	Both small and large fibre neuropathy

\*Either dorsal test result or plantar test result, and scored accordingly since sum of multiple applications.

- Evaluation of feasibility that a 10-point/cm visual analogue scale (as instructed by manufacturer) can be applied for Medipin in relation to degree of neuropathy, as opposed to standard yes/no quantification. A three-option scoring system (sharp sensation, dull sensation, absence of sensation) applied earlier with pinprick testing will also be recorded (McNeely et al, 1995).
- Relative performance/concordance achieved with 10g monofilament depending on number of tests and locations included in the assessment. This will be application of the monofilament 4x on the dorsal part of the hallux versus application once on five locations on the plantar side of the foot.

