#### 8.2 SAMPLE SIZE CALCULATION

Since Medipin and monofilament do not assess the same nerve types, a true concordance study cannot be conducted. Hence a sample size is calculated for the prevalence of diabetic neuropathy being present. For the sake of a sample size calculation the assumption is that both tests will detect diabetic neuropathy in a conservative 10% of the sampled population. In the literature a ~20% prevalence of diabetic neuropathy in diabetics is reported but many of these reports are from nearly 30 years ago and therefore a more modest percentage is assumed here. Since it is not expected that the concordance will be high due to the different fibres being tested, calculation of a sample size with sufficient power based on a hypothetical concordance rate is not included here.

Using an online calculator, https://sampsize.sourceforge.net/iface/, with the predetermined criteria of a population of 160,000, 95% confidence interval, and precision of 5%, the required sample size is 139 patients.

Subject to submission of an amendment and appraisal of how patient recruitment into the initial cohort fares, we would like to extend the study to detect 2.5% precision. Again assuming 10% prevalence (which will be reviewed once initial 139 patients have been recruited), 95% confidence interval, and the stricter 2.5% precision, a revised new total of 552 patients will be required.

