#### 8.3 PRIMARY OUTCOME STATISTICS

The Medipin result and monofilament result (either dorsal or plantar outcome) will be presented with descriptive statistics to show percentage of patients with LOPS / DN.

Test	DN Absent	DN Present
10g Monofilament test plantar side, five	Score of 9 or 10 (out of 10)	Score of 8 or lower
plantar locations on both left and right		
foot		
10g Monofilament test: four applications	Score of 3.5 or higher (out of 8).	Score of 3 or lower
on dorsal side of hallux, proximal to	Recognising that score 3.5 to 5	
toenail, on both left and right foot	considered elevated risk of DN in	
	original reference article.	
Medipin test: one application on dorsal	Sensation in both feet (either 'dull'	No sensation in one or
side of hallux, proximal to toenail, on	or 'sharp' sensation, and score of	both feet
both left and right foot	above 0 out of 10)	

Table 6, Definition and score cut-offs for different DN tests (based on published papers).

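### The primary endpoint and Table 2 read sensory test results as diagnoses of neuropathy, but nothing planned verifies neuropathy, so a higher Medipin rate fits either higher sensitivity or lower specificity

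*Protocol*

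**What the plan says.** Section 2.1 (and the summary) names the primary endpoint: "Respective detection rate of diabetic neuropathy determined by use of Medipin and standard care device (10g monofilament". Section 8.3 says the Medipin and monofilament results "will be presented with descriptive statistics to show percentage of patients with LOPS / DN", and Table 6 sorts each result into DN absent or DN present.

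Table 2 in section 2.2 crosses the two devices. A patient who feels the monofilament but not Medipin is labelled "Only small fibre neuropathy". The opposite discordant cell is labelled as large fibre neuropathy only. No cell allows for a false positive.

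The visit (section 5.2, Table 5) consists of history and demographics, EQ-5D-5L, the MNSI symptom questionnaire, two monofilament procedures and Medipin. Section 1 mentions nerve conduction and skin biopsy as more sensitive, but neither is planned. Section 8.4 uses the MNSI score mainly to describe the cohort, with an optional regression. Only people with diabetes are eligible (section 4.2).

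**The concern.** A positive sensory test and a case of diabetic neuropathy are different things unless the test is perfectly specific. Without a reference measurement, a test that gives more false positives appears to detect more disease. The Table 2 rule would then enter those false positives as small fibre neuropathy found by Medipin and missed by standard care. This is not a detail that an analysis plan could supply, because no analysis can recover a reference measurement that was never taken.

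The protocol's own background shows that positivity is not specific to diabetic neuropathy. In one cited study, "11.7% of women with normal fasting glucose, 14.4% of women with impaired fasting glucose (IFG), and 18.3% of women with diabetes had LOPS", and section 1 adds that there were "no statistically significant differences in the prevalence of monofilament insensitivity between non-diabetics and diabetics".

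At stake is the conclusion that readers will look for: whether Medipin finds neuropathy that the monofilament misses. The lay summary and section 1 both point towards earlier detection as the hoped-for benefit.

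**Working it through.** **1. The plan's own figure.** Section 8.2 gives "a population of 160,000, 95% confidence interval, and precision of 5%, the required sample size is 139 patients", assuming 10% positive. With n0 = z²p(1−p)/d² and z = 1.96, p = 0.10, d = 0.05, n0 = 138.29. The finite-population correction n0/(1 + n0/160,000) gives 138.17, rounded up to 139. At d = 0.025, n0 = 553.17, corrected to 551.26, rounded up to 552. Both figures reproduce. The sample size is sound for estimating a proportion test-positive; the fault lies in what that proportion is called.

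**2. What the data can identify.** For each test, with prevalence p, sensitivity Se and specificity Sp:

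rate positive = p·Se + (1−p)(1−Sp).

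The trial observes only the left-hand side. Take a Medipin rate of 20% (assumed for illustration). It fits all of these:

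| Prevalence | Sensitivity | Specificity | Share of positives that are true |
|---|---|---|---|
| 10% | 50% | 83.3% | 25% |
| 10% | 90% | 87.8% | 45% |
| 20% | 90% | 97.5% | 90% |
| 20% | 100% | 100% | 100% |

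First row: (0.20 − 0.10×0.50)/0.90 = 0.167, so Sp = 0.833; true share = 0.05/0.20 = 25%. Nothing in the planned data separates the rows. Kappa and McNemar do not help, since both are functions of the same two-by-two table of positivity.

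**3. The positivity rules differ (sections 5.3 and 8.3).**
- Medipin: one application per foot; no sensation in either foot makes the patient positive.
- Plantar monofilament: a non-response is repeated twice before it counts, and a score of 8 or lower out of 10 requires at least two failed sites.
- Dorsal monofilament: eight applications, positive at a score of 3 or lower out of 8.

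A single missed stimulus can therefore make a patient positive on Medipin but not on the plantar or dorsal test. If an unaffected foot missed one prick 5% of the time (assumed, feet independent), 1 − 0.95² = 9.75% of unaffected patients would be classed DN present; at a 1% miss rate it would be 1 − 0.99² = 1.99%. Against this, Table 6 counts a dull sensation as DN absent, which makes the Medipin rule stricter. Equal specificity cannot be presumed, but the direction of any difference is open.

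**4. What unequal specificity would do.** Assumptions, none of them in the protocol: p = 10%, both tests 80% sensitive, errors independent given disease status, monofilament Sp 95%, n = 139, exact two-sided McNemar at 5%.

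- Monofilament rate: 0.10×0.80 + 0.90×0.05 = 12.5%.
- Medipin Sp 90%: 0.08 + 0.90×0.10 = 17.0%; McNemar significant in about 20% of simulated trials.
- Medipin Sp 85%: 0.08 + 0.90×0.15 = 21.5%; significant in about 60%.

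At 60% sensitivity for both tests, the two figures are about 18% and 57%.

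The Medipin-only cell is p·Se(1−Se) + (1−p)·Sp(monofilament)·(1−Sp(Medipin)):
- Medipin Sp 90%: 0.016 + 0.90×0.95×0.10 = 0.1015, or 14.1 of 139 patients, of whom 0.0855×139 = 11.9 have no neuropathy.
- Medipin Sp 85%: 0.016 + 0.90×0.95×0.15 = 0.1443, or 20.1 of 139, of whom 0.1283×139 = 17.8 have no neuropathy.

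Table 2 would label all of them as small fibre neuropathy.

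**The case against.** The strongest defence is that the labels are operational and disclosed. The endpoint is the rate found by use of each device, the approach is declared pragmatic, and Table 6 states explicit cut-offs. The primary analysis is descriptive, the sample size is set for precision, and no superiority claim is planned. McNemar is secondary, and section 8.4 already describes it as comparing distributions of outcomes. Sections 2.2 and 8.2 say the devices test different fibres, so disagreement is expected. The MNSI, with its small- and large-fibre items and a question on prior diagnosis, could give indirect corroboration through the optional regression.

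Much of this stands, and it limits the point to labels and permitted inference. It does not remove the point. Pragmatism and different fibre targets explain the choice of tests; neither verifies a positive. Different targets account for disagreement only if each positive is true, which is what goes untested. The MNSI is self-reported and has no cut-off or reference role in the plan.

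Two criticisms of the illustration are also fair. It uses one shared disease state, whereas the protocol posits two pathologies, and equal true yield is built into it. The identifiability argument in step 2 needs neither assumption.

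Stronger readings are tempting but unsupported:
- A reader might take 11.7% as this trial's false-positive rate, or its ratio to 18.3% as the share of positives that are background. It comes from women with normal fasting glucose in one study whose sites and cut-off the protocol does not give, and some of those women may have had neuropathy of another cause.
- A reader might fault the 10% planning value for lying below 11.7%. The plan makes no comparison with a non-diabetic rate.
- A reader might object that a design called controlled has no group without diabetes. The word can mean the within-patient comparison with standard care.

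**Conclusion.** The point holds as one of labelling and inference. The trial can estimate, with the stated precision, the proportion positive on each procedure and how often the procedures disagree. It cannot show that either device detects more diabetic neuropathy, and the Table 2 rule would count any false positive as disease. This follows from the absence of a verifying measurement and rests on no assumed figure.

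Its size in this trial is unknown. Under the stated assumptions, a significant McNemar result without any extra true case would occur in about 20% of trials at 90% Medipin specificity and about 60% at 85%, against 95% for the monofilament. A reader might infer from this range that Medipin is the less specific test; the protocol contains no evidence either way. The cited 11.7% shows only that monofilament positivity is not specific to diabetic neuropathy.

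**What to change.** - **Summary, 2.1, 8.3 and Table 6:** replace the detection rate and the DN present/absent labels with the proportion test-positive, reported separately for Medipin, plantar monofilament and dorsal monofilament.
- **Table 2:** label the cells Medipin positive only, monofilament positive only, both positive and neither positive.
- **8.4:** state that kappa and McNemar compare positivity, and that a higher Medipin rate will not be read as more or earlier neuropathy detected.

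This changes wording only; tests, patients, sample size and computations stay as they are. The price is a more modest claim for the device. If the sponsor wants to keep a detection claim, an independent reference measurement would be needed, at least in a subsample, which does add cost.
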